Ketamine is an NMDA antagonist that, at high doses (>1mg/kg), induces dissociative anesthesia with minimal effects on ventilation and airway reflexes (Gorlin). Low dose ketamine infusions (<0.3mg/kg/hour) have proven efficacy for reducing pain scores as well as reducing post-operative opioid consumption in a wide variety of surgical procedures (Gorlin JAnesthClinPharm 2016). Furthermore, even at anesthetic doses, ketamine has no negative effect on pharyngeal muscle tone (Drummond BJA 1996). For these reasons, low dose ketamine may be an ideal analgesic adjunct for patients undergoing gastric bypass. Sollazzi et al demonstrated lower PACU pain scores and opioid consumption in patients undergoing gastric bypass who received a combined ketamine/clonidine infusion in the operating room (Sollazzi SurgObesRelDis2009). However, to our knowledge, there have been no studies looking at combined intraoperative and postoperative ketamine infusions for gastric bypass.

Our hypothesis states that in laparoscopic gastric bypass patients intraoperative ketamine infusion combined with continuation for twenty-four hours post-surgery provides superior pain control and decreases post-operative opioid use versus standard non-ketamine therapy.

Study Objectives

Primary Objective

- To assess the efficacy of a standardized bolus and infusion dose of intravenous ketamine on perioperative opioid requirements in gastric bypass surgical patients.

Secondary Objective

- To assess the efficacy of a standardized bolus and infusion dose of intravenous ketamine on perioperative pain scores, patient satisfaction with pain management, and length of stay in hospital in gastric bypass surgical patients. To assess the safety and tolerability of intravenous ketamine by examining presence of post-operative nausea and vomiting, pruritus, sedation, agitation, hallucinations, delirium, and adverse respiratory events.

Study Design and General Description

- **Randomization after consent is obtained to either ketamine or standard therapy**

- **Standard therapy group study protocol**
 - Calculation of ideal body weight (IBW) – see calculator
 - Pre-operative dexamethasone 4mg IV
 - Pre-operative midazolam 1-2mg IV for anxiolysis at discretion of anesthesiologist
 - Induction of anesthesia
 - Propofol 2-3mg/kg IV (IBW) at discretion of anesthesiologist
 - Fentanyl 1mcg/kg IV (IBW)
 - Neuromuscular blockade with succinylcholine and/or rocuronium at the discretion of the anesthesiologist

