- **Pre-operative data**
 - Age
 - Gender
 - Height, weight, BMI
 - ASA classification
 - Medical problems
 - Surgical history
 - Home medications
 - Home CPAP?
 - Allergies

- Presence of *active* chronic pain? If so, what is it?
- Currently taking opioids on a daily basis for the past 1 month or greater? If so, quantitate daily dose in morphine equivalents (ME)
- **Post-operative data**
 - Total opioid dose in ME from OR to discharge
 - May look separately at OR, PACU, 1st 24 hours, 2nd 24 hours
 - Pain scores over course of hospitalization
 - May look separately at PACU, 1st 24 hours, 2nd 24 hours
 - PONV
 - Need for additional anti-emetics during hospitalization
 - Pruritus
 - Need for anti-histamines during hospitalization
 - Sedation
 - Average RASS scores 1st 24 hours
 - Any episodes of (-)3 or worse RASS
 - Any evidence of sedation in nursing notes
 - Agitation
 - Average RASS scores 1st 24 hours
 - Any episodes of (+) RASS scores
 - Any evidence of agitation from nursing notes
 - Hallucinations
 - Ketamine drip d/c
 - Review nursing and Pain Service notes
 - Delirium
 - Ketamine drip d/c
 - Review nursing and clinical notes
 - Adverse respiratory events
 - Rapid response events
 - Naloxone administration
 - Change in level of care (intermediate or ICU)
 - Review of nursing notes and clinician progress notes
 - Length of Stay
 - Hours
 - Use of CPAP while inpatient. Y/N
 - Patient satisfaction with pain management questionnaires
 - First questionnaire will be completed by the patient at the time of discharge from the hospital.
 - Second questionnaire will be completed by the patient at the postoperative visit with the surgeon or via phone contact with the patient on or around 30 days after surgery if there has been no postoperative visit.

Subject Selection Enrollment and Withdrawal

Inclusion Criteria

- Patients > or equal to 18 years old and < 70 years old undergoing laparoscopic gastric bypass at Mayo Clinic Arizona
- BMI > or equal to 35
- Consent obtained as per Mayo Clinic policy

Exclusion Criteria

- Intolerance to ketamine
- History of schizophrenia, schizoaffective disorder or other psychiatric diagnosis with psychotic features
- Presence of unstable cardiovascular disease. (The presence of acute coronary syndrome, unstable angina, hypertension emergency, acute TIA or stroke.)
- Presence of acute elevation of intracranial or intraocular pressure
- Presence of seizure disorder
- History of substance abuse or addiction
- Creatinine > 1.5

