- End-stage liver disease
- Pregnancy
- **Patients with chronic pain and/or chronic opioid therapy:**
 - In order to more closely replicate the study patient population of interest we will not exclude this patient population
 - However, we will exclude patients taking >50 morphine equivalents (ME) per day for greater than 1 month prior to surgery

Subject Recruitment, Enrollment and Screening

Appointment calendars will be screened. Those eligible will be consented by physician or study coordinator either in POE or Surgery Clinic.

Study Procedures

- **Patient Consent**
 - Patients who appear to meet the inclusion criteria and none of the exclusion criteria will be invited to participate in this study. The study will be explained to the patient, including risks and benefits by the Study Coordinator, and one of the physicians, if available.

- Each patient who agrees to participate will be required to sign and date an informed consent document prior to any study-specific testing and procedure. A copy of the signed and dated consent will be provided to the patient.
- Method for Assigning Patients to Treatment Groups
 - If the patient meets inclusion/exclusion criteria and consents to participate in the study, the morphine equivalents will be calculated by one of the investigators.
 - The REDCap database will be completed with the inclusion/exclusion criteria and morphine equivalents. REDCap will provide the randomization group for the patient.
 - The randomization group will be conveyed to the study team by the Study Coordinator.
- Data Collection and Monitoring
 - All required data is collected during the hospitalization from the electronic medical record.
 - The floor nurses will follow the already existing ketamine guidelines for Pain Service and stopping criteria.
 - The investigators will carefully monitor the subject during hospitalization for any adverse events.
- Discharge from the Hospital
 - At the time of discharge from the hospital, the patient will complete the Patient Satisfaction with Pain Management at Discharge questionnaire.
- Postoperative Visit
 - At the postoperative visit with the surgeon, the Patient Satisfaction with Pain Management questionnaire at Post-op Visit will be completed by the patient. If no postoperative visit is scheduled, this will be done via telephone contact on or around 30 days after surgery. We will allow a window of 30-60 days in case there is difficulty reaching the patient..
- Adverse events

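### The arm can be released at any time after clinic consent, with no eligibility check before induction, so patients can be dropped and replaced with the arm known

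*Combined protocol and SAP*

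**What the plan says.** All references are to the combined protocol and SAP.

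- **Consent.** Subject Recruitment, Enrollment and Screening: calendars are screened, then "Those eligible will be consented by physician or study coordinator either in POE or Surgery Clinic".
- **Randomization.** Study Design and General Description says only "Randomization after consent is obtained to either ketamine or standard therapy".
- **Allocation steps.** Study Procedures, Method for Assigning Patients to Treatment Groups, gives the order. First, "If the patient meets inclusion/exclusion criteria and consents to participate in the study, the morphine equivalents will be calculated by one of the investigators". Next, "The REDCap database will be completed with the inclusion/exclusion criteria and morphine equivalents. REDCap will provide the randomization group for the patient". Last, "The randomization group will be conveyed to the study team by the Study Coordinator". No later eligibility step follows.
- **Exclusions that can change.** Exclusion Criteria lists unstable cardiovascular disease, explained as "The presence of acute coronary syndrome, unstable angina, hypertension emergency, acute TIA or stroke". It also lists an acute rise in intracranial or intraocular pressure, creatinine above 1.5, and pregnancy. No sampling or test window is given for the last two. A further exclusion, use of more than 50 ME per day for over a month, is worded relative to surgery.
- **Start of treatment and outcome.** The ketamine bolus is given with induction, and the primary outcome is counted from induction to 48 hours after it.
- **Numbers.** Number of Subjects allows up to 45 enrolled to reach 17 per group (34 accrued), citing the randomization list and withdrawals.
- **Analysis.** Statistical Methods names a Wilcoxon rank-sum test for the primary outcome. It defines no analysis population and no rule for a patient found ineligible after allocation.

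**The concern.** Eligibility is settled once, before allocation, but it matters at induction. The plan leaves the time between the two open. During it a patient may come to meet an exclusion, withdraw, or have the operation cancelled. The study team already knows the arm by then, so the decision to keep or remove the patient can depend on it. Several exclusions concern the suitability of ketamine, so the same finding may prompt removal from the ketamine arm and pass without action in the control arm.

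What is at stake is the comparability of the groups. Suppose baseline opioid use predicts 48-hour opioid use, which is plausible but not stated in the documents. If patients whose opioid intake has risen are removed from the ketamine arm only, the patients left in that arm will tend to need less opioid whatever ketamine does. Replacing them restores the count but not the balance.

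**Working it through.** **Step 1. Order of events.** The written sequence is: clinic consent, ME calculated, REDCap completed, arm returned, arm conveyed to the team, induction. A date or place is attached only to consent. The text fits allocation at the clinic visit and allocation on the morning of surgery equally well. In neither case does it require a check between allocation and induction.

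**Step 2. Which criteria can change.**

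| Exclusion | Can it change after clinic? | Likely effect on surgery |
|---|---|---|
| Unstable cardiovascular disease | Yes, acute | Would probably cancel it in either arm |
| Acute intracranial or intraocular pressure rise | Yes, acute | Would probably cancel it in either arm |
| Creatinine above 1.5 | Yes, no sampling window | Need not stop it |
| Pregnancy | Yes, no test window | Not settled by the documents |
| More than 50 ME/day for over 1 month before surgery | Yes, but needs sustained use | Need not stop it |

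The third column is a judgement, not a statement in the documents. Arm-dependent removal is most plausible where surgery still goes ahead.

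**Step 3. The plan's own sample size.** Inputs from Sample Size and Power Calculation: P = 0.746, one-sided alpha 0.05, power 80%. Noether's formula with equal arms:

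N = (1.645 + 0.842)² / (12 × 0.25 × (0.746 − 0.5)²) = 6.18 / 0.1815 = 34.05, or 17.03 per arm.

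Power at N = 34 is Φ(√(3 × 34) × 0.246 − 1.645) = Φ(0.839) = 79.9%. The stated 17 per group reproduces.

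**Step 4. Does the enrollment allowance cover losses?** Spare places: 45 − 34 = 11, and 11/45 = 24.4%. Enrollment needed at loss rate d is 34/(1 − d): 36 at 5%, 38 at 10%, 43 at 20%, 49 at 30%. These rates are illustrations. With replacement, total losses up to 24.4% are covered.

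**Step 5. What if losses are not replaced, or patients stay in untreated?** The numbers of patients are again illustrations. In the first column, k of the 17 ketamine patients get no ketamine, behave like controls and stay in the analysis, so P = 0.5 + 0.246 × (1 − k/17). In the second, k patients in total are dropped without replacement, so N = 34 − k.

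| k | Untreated but analysed | Dropped, not replaced |
|---|---|---|
| 0 | 79.9% | 79.9% |
| 1 | 75.6% | 78.9% |
| 2 | 70.8% | 77.8% |
| 3 | 65.6% | 76.7% |

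Dropping and replacing costs little or no power, and keeping untreated patients in their arm costs more. With no analysis set stated, the easier course is therefore to remove the patient, which is the course that can introduce bias. Allocating after the check avoids most of this choice.

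**The case against.** The strongest reply is that early allocation is not stated. A reader might infer that the arm is fixed at the clinic visit, long before surgery. The documents place only consent there; they do not say when REDCap is run and do not rule out the day of surgery. That stands: the gap is an unspecified interval and a missing check, not a demonstrated delay.

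A reader might also infer that a patient with a new acute exclusion would go on to receive ketamine. The documents do not support this. Most acute events would probably stop the operation in either arm, and without induction the primary outcome window never opens. The Pre-operative data list also gathers medical problems, home medications and current opioid use, though it is not described as an eligibility check.

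The opioid criterion is narrower than it may look. A patient at or below 50 ME/day in clinic can newly meet it only if more than a month then passes before surgery. One already above 50 but short of a month would show up in the ME calculation before allocation. It is also the only exclusion worded relative to surgery.

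Finally, replacement up to 45 answers most of the worry about numbers. It does not answer who is removed, by whom, and with what knowledge of the arm.

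**Conclusion.** The point holds as a gap in the plan: allocation may be released at any time after consent, no eligibility or ME confirmation is required before induction, and patients lost in between can be dropped and replaced with the arm known. This rests on the text describing no blinding, defining no analysis set, and conveying the arm to the study team.

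The size cannot be estimated, because the documents give neither an interval nor a rate of change in eligibility. A reader might take this as a threat to power. With 11 spare places that is unlikely, unless untreated patients are kept in the ketamine arm, where one to three of 17 would bring power from 79.9% to between 75.6% and 65.6%. The main risk is selective exclusion after randomization. The change is worth making as a cheap improvement; the point does not show that the design fails.

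**What to change.** Keep consent in clinic. In Method for Assigning Patients to Treatment Groups:

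1. Add a documented confirmation, on the day of surgery, of the protocol's existing exclusion criteria and of current ME, drawn from routine pre-operative information.
2. Release the REDCap allocation only after that confirmation and before induction.
3. Count a patient who fails it, withdraws before it, or has surgery cancelled before it as a screen failure, not as a randomized patient.

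In Statistical Methods, state that all patients allocated after the confirmation are analysed in their assigned arm.

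This changes no eligibility criterion and no treatment. The cost is one procedural amendment, a sentence in the analysis section, and readying the study drug on the day of surgery instead of ahead of it. It will not prevent removals after induction; the analysis-set sentence is there for those.

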 - Orotracheal intubation
 - Maintenance of anesthesia
 - Sevoflurane/rocuronium
 - Additional doses of fentanyl 0.5-1mcg/kg (IBW) at discretion of anesthesiologist
 - Emergence from anesthesia
 - Acetaminophen 1g IV unless contraindicated
 - Ketorolac 30mg IV unless contraindicated
 - Ondansetron 4mg IV unless contraindicated
 - Suggamedex 2mg/kg or 4mg/kg dose (Actual BW) depending on twitch response per drug manufacturer's recommended protocol
 - Post-operative analgesia
 - Hydromorphone PCA 0.2mg/8 min
 - Acetaminophen 1g IV Q8 ATC x 3 additional doses
 - Ketorolac 15mg IV Q6 ATC x 3 additional doses
 - Other post-operative care as per usual surgical routine

- **Ketamine therapy group**
 - Ketamine 0.3mg/kg (IBW) bolus with induction
 - Ketamine infusion 0.2mg/kg/hr. (IBW) initiated after induction and terminated after 24 hours
 - Ketamine infusion will not be titrated

- Ketamine infusion may be terminated if the patient is having side-effects relating to the drug; Pain Service will follow the patient and assist with troubleshooting and determining the need for infusion termination
- The remainder of care will be identical to the standard therapy group

Number of Subjects

We will enroll up to 45 subjects to attain our goal of 17 subjects per group for a total of 34 accrued subjects. This is to ensure our goal is met based on the randomization list, as well as to account for any withdrawals that occur throughout the study.

Primary Study Outcome

Total cumulative perioperative opioid dose measured in morphine equivalents from induction of anesthesia until 48 hours after induction of anesthesia.

Secondary Study Outcomes

Visual analog pain scores measured from PACU arrival until 48 hours after induction of anesthesia. PONV and pruritus recorded from PACU arrival until discharge from hospital. Length of stay in hospital will be recorded. Patient satisfaction with pain management will be measured by questionnaires that patients complete at the time of discharge and at the postoperative visit with the surgeon or via telephone about 30 days after surgery.

Primary Safety Outcomes

There will be careful and continuous monitoring, intervention and recording of hemodynamics, sedation, agitation, hallucinations, delirium, and adverse respiratory events.

Standardized nursing procedures will be used including vital signs, RASS sedation scores, according to standard intensive post-surgical requirements. Standardized single dose regimen for ketamine.

Data

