 - Adverse events will be captured and monitored for the first 30 days following surgery to ensure patient safety.
- Data Entry into REDCap
 - The residents will complete data entry into the REDCap database.

Time Frame

Enrollment will be completed within 48 months.

Statistical Plan

Sample Size and Power Calculation

Our primary hypothesis is to check if the new management will keep patient to get less "48 hours morphine equivalent (mg)". A sample size of 17 in each group will have 80% power to detect a probability of 0.746 that an observation in new management group is less than an observation in control group using a Wilcoxon (Mann-Whitney) rank-sum test with a 0.050 one-sided significance level. In other words, we will arrange the total doses at 48 hours of patients from smallest to biggest. If 13 or more out of first 17 comes from the new management group, we will claim a success.

Statistical Methods

Basic patient characteristics, using mean \pm SD or median (range) for continuous variable and frequency (% percentage) for categorical data, will be summarized in a table. 2- group t-test, Wilcoxon rank sum test, Pearson Chi-square test or Fisher exact test will be used to compare the two kinds of management when appropriate. The "48 hours morphine equivalent (mg)" will be compared between the two groups using Wilcoxon Rank sum test. A p-value less than 0.05 will be treated as statistical significant. All statistical analyses will be performed by SAS version 9.4 software (SAS institute Inc, Cary NC).

Adverse Event Reporting Period

For this study, the follow-up period is defined as 30 days following surgery.

Medical Monitoring

It is the responsibility of the Principal Investigator to oversee the safety of the study. This safety monitoring will include careful assessment and appropriate reporting of adverse events. Medical monitoring will include a regular assessment of the number and type of serious adverse events

Data Security and Confidentiality

All electronic data will be stored in a password-protected database (RedCap). The data storage will be restricted to facility computers that are password protected. Relevant clinical information will be reported only with collective data with no identities revealed.

Study Monitoring Plan

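### The written success rule (13 or more of the 17 lowest totals) is not the powered Wilcoxon test: its false-positive rate is 0.26%, and its power at the planned effect is about 25–29%, not 80%

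*Combined protocol and SAP*

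**What the plan says.** Under Statistical Plan, Sample Size and Power Calculation, the planned test and effect are: "A sample size of 17 in each group will have 80% power to detect a probability of 0.746", that being the chance that a patient on the new management uses less opioid than a control patient, "using a Wilcoxon (Mann-Whitney) rank-sum test with a 0.050 one-sided significance level".

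The section then offers what it presents as the same thing in plainer terms: "In other words, we will arrange the total doses at 48 hours of patients from smallest to biggest". The decision rule follows: "If 13 or more out of first 17 comes from the new management group, we will claim a success".

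Statistical Methods says only that the 48-hour morphine-equivalent total "will be compared between the two groups using Wilcoxon Rank sum test", with p below 0.05 counted as significant. It does not mention the count and does not say whether the p-value is one- or two-sided.

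Number of Subjects says: "We will enroll up to 45 subjects to attain our goal of 17 subjects per group".

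**The concern.** The Wilcoxon test uses the rank of every patient. The count rule splits the 34 patients at the median and asks only how many ketamine patients lie below the split, so it discards the ordering within each half. Nothing in the section shows that a cut-off of 13 corresponds to a one-sided 0.05 level.

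The cut-off may come from treating 0.746 as a share of the lowest 17 (0.746 × 17 = 12.7, rounded up to 13). The plan does not say so, and this is inference. The figure 0.746 is a pairwise probability, not the expected proportion of ketamine patients in the lower half.

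At stake is how the primary outcome is called. A sponsor that follows the written rule will usually miss an effect of exactly the planned size. A sponsor that follows the Wilcoxon p-value can claim success where the protocol's only explicit definition of success says otherwise. A choice between the two made after the data are seen would be open to challenge.

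**Working it through.** **Inputs.** From Sample Size and Power Calculation: 17 per group, P = 0.746, one-sided alpha 0.05, power 80%, cut-off 13 of the lowest 17. The documents give no distribution for the 48-hour total, so shapes are assumed wherever power is computed.

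**1. The plan's own figure.** Noether's formula with equal allocation gives

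N = (z_alpha + z_beta)² / [12 × 0.25 × (P − 0.5)²] = (1.645 + 0.842)² / (3 × 0.246²) = 34.05 in total, or 17.03 per arm.

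Power at N = 34 is Φ(√(3 × 34) × 0.246 − 1.645) = 79.9%. The stated 17 per group and 80% reproduce for the one-sided Wilcoxon test.

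**2. False-positive rate of the count rule.** With no treatment effect and no ties at the cut, the number of ketamine patients among the lowest 17 is hypergeometric. For 13 or more:

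Σ C(17,j)² / C(34,17), j = 13 to 17
= (5,664,400 + 462,400 + 18,496 + 289 + 1) / 2,333,606,220
= 6,145,586 / 2,333,606,220 = 0.0026.

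This is exact whatever the distribution. No cut-off gives 0.05:

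| Ketamine patients among lowest 17 | Null probability |
|---|---|
| 11 or more | 0.0847 |
| 12 or more | 0.0190 |
| 13 or more | 0.0026 |

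**3. Exact Wilcoxon cut-off.** Let U be the ketamine rank sum minus 153. It runs from 0 to 17 × 17 = 289, and small values favour ketamine. The exact null distribution gives P(U ≤ 96) = 0.0493 and P(U ≤ 97) = 0.0530, so the one-sided 0.05 test rejects when U ≤ 96.

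**4. Power at the planned effect.** For each shape, 200,000 trials of 17 v 17 were simulated with P(ketamine < control) set to 0.746.

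| Shape | Count rule | Exact one-sided Wilcoxon | Wilcoxon significant, rule not met |
|---|---|---|---|
| Normal shift | 26% | 83% | 57% |
| Exponential (proportional hazards) | 25% | 83% | 57% |
| Logistic shift | 29% | 82% | 53% |
| Normal, SD ratio 2:1 either way | 30% | 82% | 51% |
| Uniform shift | 14% | 83% | 69% |
| Laplace shift | 39% | 82% | 43% |

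Repeat runs move these by a few tenths of a percentage point. For the first three shapes, the expected number of ketamine patients among the lowest 17 is about 11.6 to 11.7, so the bar of 13 lies above the result the planned effect would typically produce. Under a normal shift the rule reaches 80% power only near P = 0.875.

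**5. The reverse conflict.** With ketamine patients at ranks 5–17 and 31–34 the count is 13 and the rule is met. The rank sum is 143 + 130 = 273, so U = 120 and the exact one-sided p is 0.21 (normal approximation: z = (273 − 297.5) / 29.03 = −0.84, p = 0.20). This is possible but very rare: below 0.1% of simulated trials at the planned effect.

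**6. Unequal analysed groups.** The rule's null rate changes if the split is not 17 and 17. From Σ C(18,j) C(16,17−j) / C(34,17) for j = 13 to 17, 18 ketamine v 16 control gives 0.0075. Reversing the groups (16 v 18) gives 0.0008.

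**The case against.** The strongest reply is that Statistical Methods already names the Wilcoxon test with p below 0.05 and contains no count. The count appears only in the sample-size section and is introduced as a paraphrase, so it can be read as a failed plain-language gloss. On that reading the 5% error rate and the planned power are untouched. It is true that the power calculation is correct and that an analysis following Statistical Methods would keep it. But the count sentence is worded as a commitment, it is the only sentence that defines success, and nothing ranks the other section above it. Even as a gloss it is false, because it describes a 0.26% test as a 5% test.

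A second reply is that 25–29% is too precise when the dose distribution is unknown. This stands in part. The figure belongs to the normal, exponential and logistic shapes. Across all the shapes tried, power runs from 14% to 39% and discordance from 43% to 69%. The direction does not change, and the 0.26% does not depend on shape.

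A third is that the dependence on 17 v 17 is minor, because the surplus enrolment is there to reach that number, and a critical value of U has the same limit. This is fair: the point is secondary, and any quoted U value is only an illustration. A Wilcoxon p-value, by contrast, adapts to the numbers actually analysed.

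**Conclusion.** The concern holds. The decision threshold is wrong as written: the count rule is neither equivalent to the powered test nor calibrated to its alpha. Its false-positive rate is 0.26% (exact for 17 v 17 with no ties at the cut). Its power at P = 0.746 is about 25–29% under the normal, exponential and logistic shapes, and 14–39% over the wider set tried, against 82–83% for the exact one-sided Wilcoxon test. Under those three shapes the two criteria disagree in more than half of trials at the planned effect, almost always with the Wilcoxon test significant and the rule not met. The sample size of 17 per group is not in question for the one-sided test. Because the fault decides whether the primary outcome is declared positive, it must be fixed before analysis.

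**What to change.** In Sample Size and Power Calculation, delete the sentence that begins the restatement ("In other words, we will arrange the total doses at 48 hours of patients from smallest to biggest") and the success rule that follows it. State one success criterion there and in Statistical Methods: the Wilcoxon rank-sum p-value on the 48-hour total, with alpha and sidedness written out. Sidedness has to be explicit because Statistical Methods now omits it and the 80% power holds only for the one-sided test (Noether's formula gives 70% two-sided).

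If an illustration is wanted, use the exact critical value: with 17 v 17 and no ties, one-sided p ≤ 0.05 when the ketamine U is 96 or less out of 289. Label it as applying to those group sizes only.

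The cost is a wording change in the statistical plan. No patients, data or procedures are affected.

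### The primary test leaves out baseline daily opioid dose, which is recorded before allocation; adjusting for it is a cheap improvement of uncertain size, not the repair of an error

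*Combined protocol and SAP*

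**What the plan says.** The primary outcome is the cumulative opioid dose in ME over the 48 hours that start at induction (Primary Study Outcome). Under Statistical Methods, this total "will be compared between the two groups using Wilcoxon Rank sum test". No covariate, stratum or adjusted analysis of it appears anywhere in the document.

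Patients with chronic pain or on chronic opioids are kept in on purpose: "In order to more closely replicate the study patient population of interest we will not exclude this patient population" (Exclusion Criteria). The limit is stated next: "However, we will exclude patients taking >50 morphine equivalents (ME) per day for greater than 1 month prior to surgery". Among long-term daily users, the baseline dose can therefore run up to 50 ME/day.

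The pre-operative data list asks whether the patient is "Currently taking opioids on a daily basis for the past 1 month or greater" and, if so, records the daily dose in ME. Under Method for Assigning Patients to Treatment Groups, "The REDCap database will be completed with the inclusion/exclusion criteria and morphine equivalents", and REDCap then returns the group. The text does not say whether the randomization list is stratified on ME.

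The sample size section sizes the trial at 17 per group for 80% power, with a probability of 0.746 that a new-management total is below a control total, using a "rank-sum test with a 0.050 one-sided significance level". It then restates the test as a count: success if at least 13 of the 17 smallest totals belong to the new-management group. The analysis rule is "A p-value less than 0.05 will be treated as statistical significant", with no side named.

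**The concern.** Baseline daily ME has the same unit as the outcome, is known before allocation, and is a plausible predictor of how much opioid a patient receives over 48 hours. If it does predict the total, a plain rank-sum test treats that explainable variation as noise. Removing it would raise power in a 34-patient trial that is sized with no margin. It would also keep the comparison fair if chance puts more daily users in one arm. If daily users are rare, or little of the home dose shows up in the 48-hour total, there is almost nothing to gain and a little to lose.

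**Working it through.** **1. The plan's own figure.** Inputs from the sample size section: P = 0.746, 17 per arm (N = 34), one-sided α = 0.05, power 80%. Noether's formula with equal arms:

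N = (1.645 + 0.842)² / [12 × 0.25 × (0.746 − 0.5)²] = 34.05, or 17.03 per arm.

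Power at N = 34: Φ(√(3 × 34) × 0.246 − 1.645) = Φ(2.484 − 1.645) = 79.9%. The stated figure reproduces. Two-sided, the same formula gives 70.0%, so the sizing is one-sided.

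**2. What adjustment could add: formula.** If baseline ME explains a fraction R² of the variation, 2.484 is divided by √(1 − R²). One-sided power becomes 83.5% at R² = 0.1, 87.1% at 0.2 and 90.7% at 0.3. Simulated gains under a latent normal model are smaller: about 2, 4–5 and 5–8 points. At R² = 0, adjustment costs about 1 point.

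**3. What adjustment could add: simulation in ME units.** All inputs in this step other than P, n and α are assumptions.
- Perioperative total: lognormal with a stated mean and CV.
- Daily users: a stated share, with home doses uniform on 10–50 ME/day.
- Carry-over: 2 days × carry-over fraction × home dose is added to the total.
- Drug effect: a multiplier on all opioid, set so that P = 0.746.
- Tests: Wilcoxon against Quade's rank analysis of covariance (rank outcome and baseline ME over all 34 patients, regress one on the other, compare the residuals by t with 32 df).

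The Wilcoxon test has 82–83% power at mean 50, CV 0.6. Change in one-sided power with Quade, in points, at 25 / 50 / 100% carry-over:

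| Daily users | Mean 50, CV 0.6 | Mean 100, CV 0.6 | Mean 100, CV 1.0 |
|---|---|---|---|
| 10% | −0.2 / +1.7 / +5.4 | −0.9 / −0.4 / +1.9 | −1.0 / −0.9 / +0.4 |
| 20% | +0.7 / +4.6 / +9.6 | −0.7 / +0.6 / +3.8 | −0.7 / +0.2 / +2.3 |
| 30% | +1.6 / +6.2 / +12.5 | −0.1 / +1.7 / +7.1 | −0.8 / +0.6 / +4.4 |

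A repeat run of the last column at full carry-over gave about +0.5, +2.5 and +4, so differences of half a point are simulation noise. At 5% users with mean 50 and CV 0.6, the change is −0.5 / +0.6 / +2.5. With no carry-over, about 1 point is lost.

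**4. A coarse covariate.** Only daily users have a dose listed among the pre-operative data. Suppose a further 20% of patients use opioids intermittently and are coded 0 (mean 50, CV 0.6). The change is then −0.8 to +2.2 at 5% daily users, −0.3 to +4.1 at 10%, +0.3 to +8.1 at 20% and +1.0 to +10.7 at 30%.

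**5. Type I error.** Averaged over unstratified randomization, both tests reject 4.7–5.2% of the time under no effect. A difference appears only conditional on an uneven split. The chance that ketamine gets at least 3 fewer users than control is 2.4%, 7%, 14% and 17% at 5, 10, 20 and 30% users. Given that split, no drug effect, and mean 50 with CV 0.6, Wilcoxon rejects 9–10% (25% carry-over) to 16–19% (100%), and Quade 4–5%. In the mirror split, Wilcoxon rejects 0.1–2.2% and Quade about 5%.

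**6. How many users there might be.** With user share q among 34 patients, the chance of at most two users is (1−q)³⁴ + 34q(1−q)³³ + 561q²(1−q)³². At 5% this is 0.175 + 0.313 + 0.272 = 0.76. At 10% it is 0.33 and at 20% 0.02. The chance of at most one is 0.49 at 5% and 0.13 at 10%.

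**7. The counting rule.** The exact null probability that at least 13 of the 17 smallest totals come from one named arm is the sum over k = 13 to 17 of C(17,k)·C(17,17−k)/C(34,17) = 0.0026. The rule is therefore not the 0.05 rank-sum test. Because it ranks raw totals, it would also conflict with any adjusted primary test.

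**The case against.** The strongest reply is that nothing here is wrong: the planned test is valid, the sample size reproduces, and the choice between Wilcoxon and rank covariance is a design preference. That stands.

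It can also be said that the documents fix neither the sign nor the size of the gain. That stands too. The user share is unknown, and the exclusions for addiction history and for more than 50 ME/day may keep it low. Continuation of home opioids after surgery is not described. The larger gains depend on a small perioperative total with little spread. In the other direction, letting ketamine act only on the acute part of the total would raise the gains.

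With one or two users, the regression slope rests on one or two patients, so a fallback that applies only when there are no users at all is not enough. The fix below therefore sets a minimum count.

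Three stronger readings are tempting and are not supported:
- *The plain test inflates false positives.* It does not on average. The 9–19% rates hold only given an unfavourable split, and the mirror split pulls the rate below 5%. If REDCap already stratifies on ME, which entering ME before the group is issued would allow, such splits largely do not arise. Entering ME at that step is equally consistent with a check of the 50 ME/day exclusion.
- *The trial is underpowered without adjustment.* At the one-sided level used for sizing, it is not.
- *Daily users are in the trial in numbers that matter.* The documents make them eligible and give no count.

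**Conclusion.** This is a missed improvement, not an error. A baseline value that is already collected and is in the unit of the outcome goes unused in the primary test. At 17 per arm, one-sided 0.05, P = 0.746 and 5–30% daily users, adjusting for it changes power by between about −1 and about +13 points. The low end applies if baseline ME does not predict the total, if users are few, or if 25% of the home dose carries over into a large or variable total. The high end needs 30% users, full carry-over, and a perioperative mean of 50 ME with CV 0.6. With mean 100 ME and CV 1.0, full carry-over yields only about +0.5, +2.5 and +4 points at 10, 20 and 30% users. User share, home-dose distribution, carry-over, mean, CV and where the drug acts are all assumptions. Confidence is high that the variable is unused and moderate that using it would help. The case for acting is that about 1 point is at risk against a possible gain of several, at almost no cost.

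**What to change.** Before any outcome data are examined, amend the Statistical Plan as follows:

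- Make the primary test a Quade rank analysis of covariance of the 48-hour total on baseline daily ME (0 if not a daily user), at the one-sided 0.05 level used for sizing. State that side in the p < 0.05 rule.
- Keep the plain Wilcoxon test as a named sensitivity analysis. Make it primary if fewer than a pre-stated minimum of daily users is enrolled, for example 3 across both arms, counted blind to outcome. With that minimum, Wilcoxon would remain primary in about 76% of trials at 5% users, 33% at 10% and 2% at 20%.
- Delete the rule that counts 13 of the 17 smallest totals, so that there is one decision rule.
- State whether REDCap randomization is stratified on ME. If it is, include those strata in the analysis.

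The cost is SAP wording and a few lines of SAS. No new data, visits or patients are needed. The downside is about 1 point of power if baseline ME is not prognostic, and a coarse covariate that codes intermittent users as 0.
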